Prior to the Pegloticase + MTX Treatment Period, subjects will begin taking at least 1 standard gout flare prophylaxis regimen (i.e., colchicine and/or nonsteroidal anti-inflammatory drug and/or low-dose prednisone ≤ 10 mg/day) per protocol beginning ≥ 1 week before the first dose of pegloticase, continuing for at least 6 months per American College of Rheumatology guidelines (FitzGerald et al, 2020). For IR prophylaxis, fexofenadine (180 mg orally) and prednisone (50 mg orally) will be taken the night before each pegloticase infusion; fexofenadine (180 mg orally), famotidine (20 mg orally), montelukast (10 mg orally) and acetaminophen (1000 mg orally) will be taken the morning of each pegloticase infusion; methylprednisolone (125 mg intravenous [IV]), over an infusion duration between 10 and 30 minutes, will be administered prior to each pegloticase infusion.

During the Pegloticase + MTX Treatment Period, pegloticase 8 mg will be administered IV every 2 weeks from Day 1 through the Week 22/Week 46, after all predose trial visit assessments have been completed at each visit. The date, start and stop time of infusion will be recorded.

During the Pegloticase + MTX Treatment Period, subjects will be instructed to inject MTX weekly on the same day each week, within 1 to 3 days prior to each pegloticase infusion (on the weeks when pegloticase is administered); however, if a subject does not do so, MTX must be injected ≥ 60 minutes prior to each pegloticase infusion. One additional weekly dose of MTX will be injected after the last pegloticase infusion for subjects who have not stopped pegloticase due to individual subject sUA discontinuation criteria. If the subject discontinues pegloticase due to the stopping rule or other reason, MTX and folic acid should also be discontinued.

After Day 1, if a subject becomes unable to tolerate MTX, the folic acid dose can be increased, an alternative folate supplement may be used and/or the MTX dosage may be reduced or discontinued based on pre-defined criteria (Section 9.4.6.3.2.2) and the subject may remain in the trial and continue pegloticase infusions. Every attempt should be made to re-start the MTX in subjects once their MTX-associated symptoms have improved or their laboratory tests have normalized.

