During the Pegloticase + MTX Treatment Period, subjects will be instructed to inject MTX weekly on the same day each week, within 1 to 3 days prior to each pegloticase infusion (on the weeks when pegloticase is administered); however, if a subject does not do so, MTX must be injected ≥ 60 minutes prior to each pegloticase infusion. One additional weekly dose of MTX will be injected after the last pegloticase infusion for subjects who have not stopped pegloticase due to individual subject sUA discontinuation criteria. If the subject discontinues pegloticase due to the stopping rule or other reason, MTX and folic acid should also be discontinued.

After Day 1, if a subject becomes unable to tolerate MTX, the folic acid dose can be increased, an alternative folate supplement may be used and/or the MTX dosage may be reduced or discontinued based on pre-defined criteria (see [Section 9.4.6.3.2.2](#) for detailed instructions) and the subject may remain in the trial and continue pegloticase infusions. Every attempt should be made to re-start the MTX in subjects once their MTX-associated symptoms have improved or their laboratory tests have normalized.

The Investigator will review the subject clinical status and [CCI](#) ([Appendix 17.8](#)) at Week -6; prior to pegloticase infusion at the Week 24 and Week 36 Visits (subjects who may gain further benefit beyond 12 infusions and elect to receive pegloticase + MTX during the Optional Pegloticase + MTX Extension Period); and at the End of Pegloticase (if applicable) and Week 24 or 48/End of Trial/Early Termination Visits.

After the Week 24 or 48 Visit (or End of Pegloticase Visit [if applicable]) or upon pegloticase discontinuation, subjects should resume regular care for gout per the judgment of the treating physician, including resumption of urate-lowering therapy, if appropriate.

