9.4 Treatments

9.4.1 Treatments Administered

9.4.1.1 Methotrexate

During the MTX Run-in Period, which begins 6 weeks prior to the first dose of pegloticase, subjects with eGFR ≥ 45 mL/min/1.73 m² will inject SC MTX weekly at a starting dose of 15 mg

at Weeks -6 and Week -5 increasing to 25 mg at Week -4 and continuing weekly throughout the trial. Subjects with eGFR ≥ 30 and <45 mL/min/1.73 m² will inject SC MTX weekly at a starting dose of 10 mg at Week -6 and Week -5 increasing to 15 mg at Week -4 and continuing weekly throughout the trial. If a subject becomes unable to tolerate MTX at 25 mg doses, the folic acid dose may be increased from 1 to 2 mg/day and/or the MTX dosage may be decreased to 20 or 15 mg, but to no less than 15 mg. Subjects who cannot tolerate MTX at a minimum dose of 15 mg during the MTX Run-in Period will be considered MTX Run-in Screen Failures, regardless of their Baseline eGFR.

During the MTX Run-in Period, if a dose is missed, it should be injected as soon as it is remembered. If it is within 48 hours of the next scheduled dose, the subject will be instructed to skip the missed dose and resume at the next regularly scheduled time. If a subject misses more than 2 doses of MTX during the 6-week Run-in Period, the Principal Investigator should contact the Sponsor to discuss eligibility of the subject for enrollment in the Pegloticase + MTX Treatment Period.

During the Pegloticase + MTX Treatment Period, subjects will be instructed to inject MTX weekly on the same day each week, within 1 to 3 days prior to each pegloticase infusion (on the weeks when pegloticase is administered); however, if a subject does not do so, MTX must be injected ≥ 60 minutes prior to each pegloticase infusion. One additional weekly dose of MTX will be injected after the last pegloticase infusion for subjects who have not stopped pegloticase due to individual subject SUA discontinuation criteria. If the subject discontinues pegloticase due to the stopping rule or other reason, MTX should also be discontinued.

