9.5.8.4 End of Pegloticase Visit

Subjects who end pegloticase infusions prior to Week 22 will complete the End of Pegloticase Visit procedures within 2 weeks of their final infusion. Subjects are especially encouraged to complete trial visits at the trial site for key efficacy and safety assessments at Weeks 10, 12, 14, 20, 21, 22, 23 and 24/End of Trial/Early Termination, so that sUA and other key assessments can be completed. During visits between these key efficacy and safety collection visits, in subjects who have stopped infusions, subjects may complete trial visits in person or via a telephone visit to collect AE, concomitant medication and gout flare information (see [Section 9.3.3.1.1](#)).

For subjects who agree to continue trial visits after the End of Pegloticase Visit, the 30-Day Post Treatment Follow-up Visit will be captured as part of the continued visits; however, if the last trial visit is <30 days posttreatment, the 30-Day Post-Treatment Follow-up phone call/email will still be required.

The following procedures will be completed at the End of Pegloticase Visit:

- Principal Investigator review of subject clinical status and treatment goals.
- Perform a targeted physical examination (at a minimum this should include heart, lungs and abdominal examination).
- Document gout flares and intensity.
- Record vital signs (blood pressure, respiratory rate, temperature and heart rate) prior to discharge (see [Section 9.5.4.4](#)).
- Obtain a urine sample for pregnancy testing from female subjects of childbearing potential.
- Obtain optional serum and urine samples from subjects who consent for future analysis.
- Obtain blood samples for hematology, clinical chemistry and hs-CRP analysis and eGFR calculation (calculated by the central laboratory).
- Obtain a urine sample for albumin:creatinine ratio.

- Obtain a blood sample (1 sample) for measurement of sUA.
- Administer MTX (subjects who have not stopped pegloticase due to individual subject sUA discontinuation criteria).
- Assess MTX compliance/reconciliation.
- **CCI** [REDACTED].
- Administer HAQ-DI, **CCI** [REDACTED]
- Record **CCI** [REDACTED].
- If handheld uric acid device is provided, assess Investigator or subject user experience with uric acid device questionnaire at any time during the visit prior to discharge from the site.
- Assess MTX compliance.
- Ask Yes/No question regarding folic acid compliance.
- Ask Yes/No question regarding gout flare prophylaxis compliance.

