9.5.8.6 Week 24 or 48/End of Trial/Early Termination Visit

Subjects who may not gain further benefit beyond 12 infusions based on the Principal Investigator's judgement or who discontinue treatment prior to Week 22 will complete the procedures outlined below.

The following procedures will be completed at the Week 24 or 48/End of Trial/Early Termination Visit.

- Principal Investigator review of subject clinical status and treatment goals.
- Perform a targeted physical examination (at a minimum this should include heart, lungs and abdominal examination).
- Document gout flares and intensity.

- Record vital signs (blood pressure, respiratory rate, temperature and heart rate) prior to discharge (see [Section 9.5.4.4](#)).
- Record weight.
- Obtain a urine sample for pregnancy testing from female subjects of childbearing potential.
- Obtain optional serum and urine samples from subjects who consent for future analysis
- Obtain blood samples for hematology, clinical chemistry and hs-CRP analysis and eGFR calculation (calculated by the central laboratory).
- Obtain a urine sample for albumin:creatinine ratio.
- Obtain a blood sample (1 sample) for measurement of sUA.
- Administer MTX (subjects who have not stopped pegloticase due to individual subject SUA discontinuation criteria).
- Assess MTX compliance/reconciliation.
- **CCI** [REDACTED].
- Administer HAQ-DI, **CCI** [REDACTED]
- Record **CCI** [REDACTED].
- Assess MTX compliance.
- Ask Yes/No question regarding folic acid and gout flare prophylaxis (for subjects who receive gout flare prophylaxis in the Optional Pegloticase + MTX Extension Period) compliance.
- Subjects who end pegloticase infusions prior to Week 24 or 48 should follow the scheduled time points and have a DECT scan at the Week 24 or 48/End of Trial/Early Termination Visits.
- Obtain blood samples for **CCI** [REDACTED].
- Obtain blood sample for **CCI** [REDACTED].
- Obtain blood samples for **CCI** [REDACTED] analysis.
- Inquire about AEs and concomitant medication use.

9.5.8.7 30-Day Post-Treatment Follow-up Phone/Email Visit

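### Two visit checklists order methotrexate for every early stopper except sUA stoppers, although methotrexate is meant to stop with pegloticase for any reason

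*Protocol*

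**What the plan says.** The order appears in two visit checklists. In Protocol 9.5.8.4 it reads "Administer MTX (subjects who have not stopped pegloticase due to individual subject sUA discontinuation criteria", and in 9.5.8.6 "Administer MTX (subjects who have not stopped pegloticase due to individual subject SUA discontinuation criteria". Only subjects who stopped under the sUA criteria are exempt.

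Attendance at these visits is wider than that exemption. For the first visit: "Subjects who end pegloticase infusions prior to Week 22 will complete the End of Pegloticase Visit procedures within 2 weeks of their final infusion". The second includes subjects "or who discontinue treatment prior to Week 22 will complete the procedures outlined below". Footnote 4 to the Schedule of Assessments (2.1) sends subjects to the first visit whether they stopped for sUA or for something else. Section 9.3.3.1 lists adverse event, physician decision, subject refusal and pregnancy among the reasons for stopping.

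The dosing sections point the other way. Section 9.1 states: "If the subject discontinues pegloticase due to the stopping rule or other reason, MTX and folic acid should also be discontinued". Section 9.4.1.1 states: "If the subject discontinues pegloticase due to the stopping rule or other reason, MTX should also be discontinued". The Synopsis has the same rule. Section 9.3.3.1.1 stops MTX and folic acid when infusions cease early, with no exception by reason, and ends MTX dispensing. Section 9.5.4.2 tells a subject who may be pregnant to stop all trial drugs.

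In the Synopsis (Trial Design), 9.1 and 9.4.1.1, the sentence directly before the stop rule grants one more weekly MTX dose. In the Synopsis that dose comes "after the last pegloticase infusion for subjects who have not stopped pegloticase due to individual subject sUA discontinuation criteria", and 9.4.1.1 has the same condition. The Synopsis dose-regimen paragraph repeats the condition with a stray *not* that reverses it.

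**The concern.** Sites work from visit checklists. A coordinator following these two would give MTX to a subject who stopped pegloticase for an adverse event, and nothing in the bullet makes the dose depend on the urine pregnancy test in the same list. Protocol 7.1.3 lists fetal death, teratogenic effects, leukopenia and thrombocytopenia among the risks of MTX. Section 9.4.1.3 ends folic acid before the End of Pegloticase Visit, or 1 week after the last infusion for completers, so the dose could fall after folate cover has ended. Unlike the Week 23 and Week 24 infusion-visit checklists, these bullets do not first ask whether MTX was injected in the past few days.

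Three clocks run from the last dose: the treatment-emergent adverse event (TEAE) window (Protocol 9.6.7), the patient-years denominator (SAP 14.2) and the reproductive follow-up (Protocol 9.5.8.7 and 9.5.8.8). A stray dose lengthens all three.

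**Working it through.** **Text comparison by type of subject**

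| Subject | Checklist bullet | Rest of the protocol | Result |
|---|---|---|---|
| Stopped early, sUA criteria | No MTX | No MTX (9.1, 9.3.3.1.1, 9.4.1.1) | Agree |
| Stopped early, other reason | MTX | No MTX (same sections; 9.5.4.2 for pregnancy) | Conflict |
| Completed 12 infusions, leaves at Week 24 | MTX | Last MTX at Week 23 (2.1); trial drug not given at Week 24 (2.1 footnote, 9.5.8.3.15) | Conflict |

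The bullets probably carry over the extra-weekly-dose sentence. That cannot explain the Week 24 visit: a subject last infused at Week 6 would be 169 − 43 = 126 days past the last infusion. Completers already have the extra dose scheduled at Week 23 (2.1 and 9.5.8.3.14), or by Week 47 in the extension (2.1).

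**Size for one early stopper**

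Inputs:
- Target days from SAP Table 8: Week 6 = 43, Week 8 = 57, Week 22 = 155, Week 23 = 162, Week 24 = 169. The visit window of 3 days either side is ignored.
- MTX is weekly, 1 to 3 days before each infusion (Protocol 9.1). Later weekly doses therefore fall 4–6 and 11–13 days after an infusion.
- Patient-years (SAP 14.2) = (later of last MTX or pegloticase dose − first pegloticase dose + 1)/365.25.
- Assumptions: last infusion on day 43; End of Pegloticase Visit at the full 14 days, day 57.

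With the bullet followed, exposure is 57/365.25 = 0.156 patient-years. Without it:

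| MTX taken after the last infusion | Last dose of either drug | Days added | Patient-years without the bullet | Ratio |
|---|---|---|---|---|
| None | Day 43 | 57 − 43 = 14 | 43/365.25 = 0.118 | 57/43 = 1.33 |
| One weekly dose | Days 47–49 | 8–10 | 0.129–0.134 | 57/49 = 1.16 to 57/47 = 1.21 |
| Two weekly doses | Days 54–56 | 1–3 | 0.148–0.153 | 57/56 = 1.02 to 57/54 = 1.06 |

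In the last row a weekly drug is given twice within 1 to 3 days. The TEAE window, last dose plus 30 days, lengthens by the days added. A Week 24 dose for an early stopper would mean restarting MTX against 9.3.3.1.1 and is not counted.

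**Size for one Week 24 completer**

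MTX before the Week 22 infusion falls on days 152–154. The next weekly dose falls on days 159–161, or on day 162 if given at the Week 23 visit.

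- Days added by a Week 24 dose: 169 − 162 = 7 to 169 − 159 = 10.
- Patient-years: 159/365.25 = 0.435 to 162/365.25 = 0.444, against 169/365.25 = 0.463.
- Ratio: 169/162 = 1.04 to 169/159 = 1.06.

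**The case against.** The any-reason stop rule is stated repeatedly, 9.5.8.4 itself refers the site to 9.3.3.1.1, and pregnancy has its own explicit order. Most investigators would withhold MTX. That is likely, but it relies on sites overriding a written dosing order, and whichever instruction they follow, they depart from another.

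Intent is also open to argument. The bullet mirrors the extra-dose sentence, and 9.4.1.3 lets folic acid run up to the End of Pegloticase Visit, which could suggest that some later MTX was foreseen. On that reading the gap in folate cover for early stoppers may be short. This stands in part: the governing text is itself unclear for early stoppers without sUA failure, and a clear gap depends on the other sentence in 9.4.1.3, which stops folic acid together with pegloticase. It does not remove the contradiction.

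For completers, *trial drug* in 9.5.8.3.15 could mean the infusion only. However, 9.4.6.1 counts MTX as a trial drug, 9.5.4.1.4 treats MTX and pegloticase alike as trial drug, and the schedule in 2.1 ends MTX at Week 23. The conflict remains.

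The 1.33 ratio is an upper-end illustration. With a last infusion at Week 20 (day 141) and a dose on day 155, it is 155/141 = 1.10. If 30 subjects were each exposed to day 162, the total would be 30 × 162/365.25 = 13.3 patient-years. One 14-day extension adds 14/365.25 = 0.038, about 0.3%. That is fair: the effect on pooled rates is negligible.

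**Conclusion.** The concern holds. Two checklists give a dosing order that other sections of the same protocol forbid, for early stoppers without sUA failure and for Week 24 completers who do not continue. The harm is to subject safety and consistent site conduct. It is at most a stray dose per affected subject, with the single-subject shifts shown above, and these rest on target visit days and a visit at the full 14 days. The number affected is unknown because the documents give no rate of stopping for non-sUA reasons. The TEAE and exposure clocks would correctly follow a dose actually given, so no analysis rule breaks. The primary endpoint and sample size are not affected. It should be corrected because the order is wrong as written and cheap to repair.

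**What to change.** Delete the MTX administration bullet from Protocol 9.5.8.4 and 9.5.8.6. Scheduled doses are kept: the extra dose falls at Week 23 or by Week 47, and subjects entering the extension are dosed at Week 24 under 9.5.8.3.15.

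In the Synopsis (Trial Design), 9.1 and 9.4.1.1, replace the sUA-only condition on the extra weekly dose with: *for subjects who complete their planned infusions (through Week 22, or through Week 46 in the extension)*. In the Synopsis dose-regimen paragraph, replace the reversed exception with the same wording and add that MTX stops when pegloticase stops early for any reason.

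This settles one case the sponsor should confirm: a subject who leaves the extension early without sUA failure gets no extra dose, in line with 9.3.3.1.1.

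The cost is wording in six places, by amendment or clarification letter. No data, endpoint or sample-size change is needed.

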9.5.8.6 Week 24 or 48/End of Trial/Early Termination Visit

Subjects who may not gain further benefit beyond 12 infusions based on the Principal Investigator's judgement or who discontinue treatment prior to Week 22 will complete the procedures outlined below.

The following procedures will be completed at the Week 24 or 48/End of Trial/Early Termination Visit.

- Principal Investigator review of subject clinical status and treatment goals.
- Perform a targeted physical examination (at a minimum this should include heart, lungs and abdominal examination).
- Document gout flares and intensity.

- Record vital signs (blood pressure, respiratory rate, temperature and heart rate) prior to discharge (see [Section 9.5.4.4](#)).
- Record weight.
- Obtain a urine sample for pregnancy testing from female subjects of childbearing potential.
- Obtain optional serum and urine samples from subjects who consent for future analysis
- Obtain blood samples for hematology, clinical chemistry and hs-CRP analysis and eGFR calculation (calculated by the central laboratory).
- Obtain a urine sample for albumin:creatinine ratio.
- Obtain a blood sample (1 sample) for measurement of sUA.
- Administer MTX (subjects who have not stopped pegloticase due to individual subject SUA discontinuation criteria).
- Assess MTX compliance/reconciliation.
- **CCI** [REDACTED].
- Administer HAQ-DI, **CCI** [REDACTED]
- Record **CCI** [REDACTED].
- Assess MTX compliance.
- Ask Yes/No question regarding folic acid and gout flare prophylaxis (for subjects who receive gout flare prophylaxis in the Optional Pegloticase + MTX Extension Period) compliance.
- Subjects who end pegloticase infusions prior to Week 24 or 48 should follow the scheduled time points and have a DECT scan at the Week 24 or 48/End of Trial/Early Termination Visits.
- Obtain blood samples for **CCI** [REDACTED].
- Obtain blood sample for **CCI** [REDACTED].
- Obtain blood samples for **CCI** [REDACTED] analysis.
- Inquire about AEs and concomitant medication use.

9.5.8.7 30-Day Post-Treatment Follow-up Phone/Email Visit

Thirty (30) days after the last MTX dose or pegloticase infusion (whichever is later), subjects will be contacted by telephone or email to review AEs, SAEs and concomitant medications. Subjects who receive at least 1 dose of MTX and are females of childbearing potential, will receive a safety follow-up phone call/e-mail approximately 4 weeks/30 days after the last dose of MTX to verify at least 1 ovulatory cycle has occurred after the last dose of MTX. If the subject has not ovulated, the subject will be requested to return to the site for a urine pregnancy test.

9.5.8.8 MTX Partner Pregnancy Follow-up

Male subjects who are non-vasectomized will be asked 3 months after MTX discontinuation regarding partner pregnancy.

9.6 Statistical Methods and Determination of Sample Size

9.6.1 Endpoints

9.6.1.1 Primary Endpoint

The primary efficacy endpoint is the proportion of Month 6 (Weeks 20, 21, 22, 23 and 24) responders, defined as subjects achieving and maintaining sUA <6 mg/dL for at least 80% of the time during Month 6.

9.6.1.2 Secondary Endpoints

The secondary endpoints are:

- The proportion of Month 3 (Weeks 10 to 14) responders, defined as subjects achieving and maintaining sUA <6 mg/dL for at least 80% of the time during Month 3.
- The proportion of subjects who experienced any of the following events from Day 1 to Week 24: IR leading to discontinuation of treatment, anaphylaxis or meeting Individual Subject sUA Discontinuation Criteria.
- The mean change from Baseline in urate deposition volume (measured by DECT) to Week 24.
- The mean change from Baseline in HAQ-DI score at Weeks 14 and 24.
- The mean change from Baseline in HAQ pain score at Weeks 14 and 24.

- The mean change from Baseline in HAQ health score at Weeks 14 and 24.

9.6.1.3 Exploratory Endpoints

The exploratory endpoints are:

9.6.1.4 CCI

The CCI are:

- The concentrations of CCI over time.
- The incidence and titer of CCI over time.
- The concentrations of CCI over time.

9.6.1.5 Safety and Tolerability Endpoints

Safety and tolerability endpoints are:

- The incidence of IRs, anaphylaxis, gout flares, MACE and the AE/SAE profile overall and potentially attributed to the combination of pegloticase and MTX.
- The mean change from Baseline in laboratory test results, including hs-CRP.
- The mean change from Baseline in vital sign results.

